## **8.2 Treatment Satisfaction Assessments**

Investigator's global satisfaction with sarecycline treatment will be assessed at Week 12 using a single question: "how satisfied are you with sarecycline treatment outcomes", with response options ranging from 'Very Satisfied' to 'Very Dissatisfied'.

## **8.3 Treatment Effectiveness Assessments**

The effectiveness of sarecycline treatment will be assessed from the perspective of Site Investigators as well the Subjects.

### ***8.3.1 Investigator Assessments***

An IGA scale of 0 (Clear) to 4 (Severe) will be used by the Site Investigators to assess the severity of a subject's facial acne at the time of study encounters. The IGA should be representative of the investigator's overall general assessment of the subject's Acne and take into account the quality, as well as the quantity, of lesions. These assessments will be done at baseline encounter to document AV severity before initiation of sarecycline treatment; the assessments will be repeated by the Site Investigators at study subject follow-up encounters at Weeks 4, 8 & 12, post-index date. The comparison of follow-up assessments to the baseline assessment will help determine treatment effectiveness. It is expected that the Investigator assessments will be conducted via in-person visits/encounters at baseline and week-12, and when in-person assessments are not feasible (owing to COVID-related travel restrictions), the assessments maybe done via virtual/remote visits. The same evaluator shall perform all evaluations for a subject during the study, as feasible.

### ***8.3.2 Study Subject Assessments - Quantitative***

The study Subjects will undertake multiple assessments to report their self-perceived severity of AV in general. These assessments will be done at baseline encounter to document the perception of AV severity corresponding to the time of initiation of sarecycline. They are then repeated by the Subjects at ensuing encounters at Weeks 4, 8 & 12, post-index date.

### Patient Global Assessment (PtGA)

This is based on the global acne severity question within ASIS (Item # 9), where the question asks the Subjects to assess the severity of acne, with a response ranging from ‘Clear’ to ‘Severe’, scored on a scale of 0 to 4. See Section 8.1 for general details on questionnaire scoring and administration.

### Patient Rating of Appearance

ASIS Item # 10 asks the Subjects to rate how their face looked because of their Acne, with a response ranging from ‘Excellent’ to ‘Bad’, scored on a scale of 0 to 4. See Section 8.1 for general details on questionnaire scoring and administration.

### Parent/Caregiver Rating of AV Severity

Parents/caregivers of children of age 12-17yrs will report their own perceived severity of children’s AV, in addition to the children providing their perceptions. This will be accomplished via a single item “Overall, how is your child’s acne on his/her face right now?”, with the 5-point likert response scales mimicking the Item # 9 in ASIS. This will be scored in the same way as the corresponding ASIS item.

#### **8.3.3 Study Subject Assessments - Qualitative**

Subjects from a small subset of study sites will be asked to record a 1-3 minute audio (using the Mobile App) narrating their perceptions of treatment benefits associated with the sarecycline, at the end of their study participation or at Week 12, whichever comes earlier. This qualitative data will be used to ascertain attributes that study Subjects associate with sarecycline treatment in an un-prompted manner.

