## 7.5 Third Follow-up & Study Close-out Encounter (Encounter # 4)

At the completion of 12 weeks ( $\pm$  4 days) post-index date, the Site Investigators and Subjects will be asked to complete the third and final follow-up data collection to close out the study. The subject encounters are expected to take place during in-person subject visits to the clinic, but remote/virtual visits will be allowed where Covid-related protocols prevent in-person visits. Subjects will be asked to drop off the third tablet/pill bottle of Seysara® (bottle # 3) supplied to them at the Wk-8 visit, be it empty or with left-over pills.

The Site Investigators will complete the following, based on the information documented in the corresponding patient medical charts and per clinical judgment guided by observing study subject via in-person or remote/virtual visit:

- Current IGA of current AV severity on the face.
- Patient treatment compliance, per sarecycline pill/tablets left over in the subject-returned bottle.
- Modifications to sarecycline treatment characteristics (e.g., change in dose, discontinuation), in the past 4 weeks, if any.

- Perceptions of sarecycline overall treatment satisfaction.
- AEs (incl. SAEs) related to or possibly related to sarecycline, observed in the past 4 weeks, as documented in the medical charts.
- Information on withdrawal from study (if occurred within the past 4 weeks).
- Newly documented changes to patient clinical characteristics, as documented in medical charts in past 12 weeks since the baseline encounter (incl. blood pressure, weight, comorbidities).
- Modifications made to concomitant medications (for AV and comorbidities) in the past 12 weeks since the baseline encounter.

In the instances when in-person subject visits take place at Week 12, for those patients for whom baseline photographic data collection was completed, corresponding Site Investigators will take photographs of patient's face to document current acne severity at Week 12.

The study Subjects will provide the following information via online survey portal or a mobile app: Perceptions of AV-related symptoms and impact of AV on emotional functioning, social functioning and activities of daily living. In a small subset of sites, clinicians will request Subjects to provide a 1–3 minute audio recording of Subject's perception of sarecycline treatment benefits experienced during the study period.

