### **14.3 Informed Consent Process**

Informed consent is a process that is initiated prior to the individual agreeing to participate in the study and continues throughout study participation.

The participating Site Investigator will ensure that written informed consent (and/or assent, if applicable) is obtained from each subject (and parent(s) or legal guardian(s), if applicable) in accordance with applicable regulations. Subjects under the age of 18 must sign the Assent Form. The subject and their parent(s) or legal guardian(s), if applicable, will be given adequate time to consider the risks associated with participation in the study. Study Subjects may provide consent/asset using online data collection portal, in case of virtual study visits/encounters in the absence of in-person visits/encounters. Each subject will provide informed consent (and/or assent if applicable and according to IRB regulations) prior to participating in any study procedures, as outlined in Section 6.3.2 of this protocol. As an addendum to the main consent form, the Subjects from a small subset of sites will be consented (with necessary assent) to allow facial photographs taken at baseline and Week 12 by their clinician at the privacy of the clinician's office and will be consented (with necessary assent) to provide a 1-3 minute testimonial of Subject's experience with sarecycline (Seysara®) at Week 12.

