### **5.3.4 Study Subject Assessments - Qualitative**

Subjects from the study sites that undertook photography tasks were also asked to record a 1-3 minute audio (using the Mobile App) narrating their perceptions of treatment benefits associated with the sarecycline, at the end of their study participation or at Week 12, whichever occurred earlier. This qualitative data is used to ascertain attributes that study Subjects associate with sarecycline treatment in an un-prompted manner.

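### The audio task is described as asking patients for treatment benefits, so its content cannot be called un-prompted, and an absence of negative remarks says nothing

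*Protocol*

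**What the plan says.** Protocol 8.3.3 asks subjects at a small number of sites for a 1-3 minute recording in the mobile app, "narrating their perceptions of treatment benefits associated with the sarecycline". It is made at Week 12 or when participation ends, if that is sooner. The stated purpose follows at once: the data are to "ascertain attributes that study Subjects associate with sarecycline treatment in an un-prompted manner".

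SAP 5.3.4 repeats the request for benefits, now in the past tense, and adds: "This qualitative data is used to ascertain attributes that study Subjects associate with sarecycline treatment in an un-prompted manner".

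Protocol 7.5, on the Week 12 encounter, has clinicians at those sites request an "audio recording of Subject's perception of sarecycline treatment benefits experienced during the study period".

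Protocol 14.3 describes the same recording differently. Subjects at those sites are to be consented to give a "1-3 minute testimonial of Subject's experience with sarecycline". Protocol 14.4 likewise speaks of audio testimonials of the subject's experience, and foresees their use in further analyses or publications once anonymised.

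SAP Section 9 plans a table summarising verbatims from site S01. It gives no coding rule and no rule for handling favourable and unfavourable content.

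**The concern.** The request and the claim made for the data sit in adjacent sentences and do not fit. The aim is to learn which attributes patients attach to the drug, and an attribute may be good or bad. The task as described asks only for the good ones. A subject with no improvement, a side effect or general dissatisfaction is not asked about any of these. Because the recording can be made when participation ends, a subject who stopped early would also be asked about benefits.

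What is at stake is how the verbatims may be read. Among the assessments described in the two documents, this is the only one in which patients speak about sarecycline itself. The ASIS and the Expert Panel Questionnaire ask about acne, the antibiotic questions concern antibiotics and resistance in general, and treatment satisfaction is asked of investigators (Protocol 8.2, SAP 5.2). Both documents also file the audio under treatment effectiveness assessments. A mainly favourable set of remarks could therefore be taken as spontaneous opinion of the drug when its direction was set by the request.

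**Working it through.** There is no plan figure to reproduce. The check is a comparison of every place that describes the recording, plus one bound on its size.

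**What is asked, and what is claimed**

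| Place | Content requested | Property claimed |
|---|---|---|
| Protocol 7.5 | Benefits, at the clinician's request | None stated |
| Protocol 8.3.3 | Benefits | Attributes, un-prompted |
| SAP 5.3.4 | Benefits | Attributes, un-prompted |
| Protocol 14.3 | Experience (testimonial) | None stated |
| Protocol 14.4 | Experience (testimonials) | None stated |
| SAP Section 9 | Not stated; table of verbatims | None stated |

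**Reasoning**

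1. The three places that describe the task itself (Protocol 7.5, Protocol 8.3.3, SAP 5.3.4) all name benefits. None mentions drawbacks, side effects or lack of effect.
2. The two places on consent and confidentiality use the wider word experience. The documents therefore disagree on the scope of the recording.
3. Un-prompted has two possible readings.
   - No direction given: the described task does not have this property, because the request names the direction.
   - No list of attributes offered: the task has this property in part. Nothing is listed, so which benefits a subject names is unaided. Whether the remark is favourable is still steered, and the stated aim is attributes, not benefits.
4. The recording is free-form, so negatives can appear. Since they are not solicited, their absence cannot be told apart from their not having been asked for.

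**Size**

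- Audio sites: 1. SAP 5.3.3 reports photography at one site, SAP 5.3.4 ties the audio to the photography sites, and SAP Section 9 names S01 only.
- Maximum subjects per site: 10 (Protocol 6.3.2).
- Total enrolment: 300 (Protocol Section 6).
- Upper bound: 1 × 10 = 10 subjects; 10 / 300 = 3.3%.

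**Endpoints:** the audio does not appear among the primary, secondary or additional endpoints in Protocol 3.2 or SAP 2.2.

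**The case against.** The strongest case on the other side has five parts.

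- **The actual prompt is not in the documents.** Protocol 7.5, Protocol 8.3.3 and SAP 5.3.4 describe the task; they are not the app script, and Appendix B reproduces only selected questionnaires. This stands. The point concerns the task as described, and the app may already be neutral. If so, the descriptions are what need correcting.
- **Un-prompted has an ordinary meaning that fits.** The questionnaires offer fixed items and the audio offers none. This stands in part: it covers which benefits are named, not the direction of the answer.
- **The word testimonial in Protocol 14.3 is not clearly neutral.** This stands. That section shows that the scope is described inconsistently; it does not show that subjects received a balanced question.
- **Unfavourable outcomes are captured elsewhere,** through adverse events, lack-of-effectiveness reports, withdrawal reasons and the full range of questionnaire answers. This is true and limits the harm. However, adverse events and lack of effectiveness are entered by the investigator, and the questionnaires ask about acne, so none of these is the patient's own account of the drug.
- **The SAP is in the past tense, so rewording may come too late.** This may be so, and the fix allows for it.

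A reader might go further and infer that the recordings cannot show negative experience, or can contain only favourable remarks. The documents do not support that: the narrative is free-form and no rule filters its content. A reader might also infer that the verbatims will be presented as spontaneous opinion beside the patient-reported results. That is conjecture. SAP Section 9 is separate from the tables in SAP 7.1, and its heading does not use the word un-prompted.

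**Conclusion.** The point holds as a mismatch between the task described and the property claimed for its data. The request is directional, so content will lean favourable. At most, the choice of which benefits to name is unaided. A lack of negative remarks in the table would not be evidence that patients had none. The recording's scope is also described inconsistently, as benefits in three places and as experience in two.

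The matter is minor. It concerns one site and at most 10 of 300 subjects, and no listed endpoint or quantitative analysis changes. The conclusion assumes that the app and the clinicians used the request as the protocol and SAP describe it. The bound of 10 assumes that the audio was confined to S01 and that the per-site cap was kept.

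**What to change.** **If recordings are still to be made:** use one neutral prompt in Protocol 7.5, Protocol 8.3.3, SAP 5.3.4 and, if its wording differs, the app. For example: *In 1-3 minutes, describe your experience with sarecycline, both what was good and what was not.* This also brings those sections into line with the scope given in Protocol 14.3 and 14.4.

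**For recordings made with a benefits prompt:**

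- delete un-prompted from Protocol 8.3.3 and SAP 5.3.4;
- state the exact prompt used;
- title the SAP Section 9 table *Benefits reported when asked about benefits*;
- draw no conclusion on overall patient experience from it.

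The cost is a sentence in the documents and possibly the app, or a changed table title. Relabelling needs no new data and no re-analysis. The one downside is that verbatims collected under a neutral prompt may be less favourable.

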#### **8.3.4 Study Subject Photographic Assessments**

Site Investigators from a subset of study sites will take photographs of facial acne of patients at baseline encounter and at Week 12, during the in-person visits. This photographic data will be used to document and depict the changes in acne severity that may be associated with sarecycline treatment in the study.

## 8.4 Additional Subject Assessments

### Parent/Caregiver Worries about Acne

The parents/caregivers of pediatric patients with AV will be asked - how worried they are about their child's acne, with a response option of 'not at all' to 'extremely', and how concerned they are about their child's ability to accomplish future goals and reach full potential due to acne, with a 5-point likert response scale of 'not at all' to 'extremely'. These questions will be asked at baseline and Week 12.

### Concern about Antibiotics and Antibiotic Resistance

Parents/caregivers and adult patients will be asked about their concerns about (themselves or their child) using antibiotics, or concerns about antibiotic resistance, with a 5-point likert response scale of 'not at all' to 'extremely'. These questions will be assessed at baseline and at Week 12.

### Understanding of Acne-related Concerns

Pediatric patients (of age 12-17) will be asked whether their parents understand their acne-related concerns, and correspondingly, the parents/caregivers will be asked whether they understand their child's acne-related concerns. This pair of questions will have a response item on a 5-point likert scale of 'not at all' to 'very much'. These questions will be asked at baseline and Week 12.

## 8.5 Compliance to Treatment

Compliance with the assigned treatment regimen will be assessed by comparing the number of doses/tablets expected to be used, based on the total number of treatment days, with the actual number used (expressed as a percentage of used/expected) at each encounter and for the study overall. The actual consumption/use of study pills/tablets will be evaluated by assessing the left-over pills/tablets in the medication bottles returned to sites/investigators by the Subjects.

## 8.6 Safety Assessments

### 8.6.1 ***Definition of Adverse Events & Adverse Drug Reactions***

An AE is any untoward medical occurrence in a patient administered a pharmaceutical product which does not necessarily have a causal relationship with this treatment. An AE can therefore be any unfavorable and unintended sign, symptom, or disease temporally associated with the use of a medicinal product, whether or not related to the medicinal product.

The Site Investigator will use the following terms to assess the severity of each AE:

- Mild: Awareness of symptoms or signs, but easily tolerated (acceptable).
- Moderate: Enough discomfort to interfere with usual activity (disturbing).
- Severe: Interferes significantly with ability to do work or usual activity (unacceptable).

A Serious Adverse Event (SAE) is any experience that suggests a significant hazard, contraindication, side effect or precaution. With respect to human clinical experience, this includes any event which:

- results in death,
- is life-threatening,
- requires inpatient hospitalization\* or prolongation of hospitalization, unless hospitalization is for:
  - routine treatment or monitoring of the studied indication, not associated with any deterioration in condition.
  - elective or pre-planned treatment for a pre-existing condition that is unrelated to the indication under study and has not worsened since the start of study drug.
  - treatment on an emergency outpatient basis for an event not fulfilling any of the definitions of a SAE given above and not resulting in hospital admission.
  - social reasons and respite care in the absence of any deterioration in the subject's general condition.
- results in persistent or significant disability / incapacity, or

- is a congenital anomaly / birth defect,
- is a significant or important medical event that, based on appropriate medical judgment, may jeopardize the subject or may require intervention to prevent one of the other outcomes listed above.

\* Hospitalization is defined as an overnight (in-patient) stay at the hospital or emergency room.

For all AEs (either related or not related to study medication), information about the outcome (resolved or ongoing) and the action taken with the study treatment (drug withdrawn, dose reduced, dose increased, dose not changed, not applicable) will be documented.

Each AE, either serious or non-serious for which a causal relationship to sarecycline cannot be excluded, will be considered as an ADR. An ADR is an injury caused by taking medication. ADRs may occur following a single dose or prolonged administration of a medicinal product or result from the combination of two or more medicinal products.

The determination of whether an AE is related to study treatment (sarecycline) will be based on information regarding the degree to which the study treatment had caused or contributed to the event and will be categorized per the following criteria:

- Related: There were good reasons and sufficient information (e.g. plausible time sequence, dose-response relationship, pharmacology, positive de-challenge and/or re-challenge) to assume a causal relationship with the study medication in the sense that it is plausible, conceivable or likely.
- Not Related: There were good reasons and sufficient information (e.g. implausible time sequence and/or attributable to concurrent disease or other drugs) to rule out a causal relationship with the study medication.

### **8.6.2 Documentation and Reporting of ADRs, Events with Fatal Outcome and Other Reportable Events**

The Site Investigator is responsible for assessing and documenting (in subject medical charts, as part of usual care) all AEs that occur at any time during the study. The Site Investigator will determine the relatedness, seriousness, and severity for each AE, which is then recorded in the

---

Adverse Events page of the eDCF, per study schedule of events (Appendix A). Following each subject encounter (be it, via in-person or remote encounters), the Site Investigator will evaluate the last 4-weeks of documentation (in subject medical charts) to report AEs and indicate whether those events resulted in stoppage or changes to dose of study medication.

Each AE that meets the definition of ADR will be recorded in the Adverse Events page of the eDCF and comprehensively documented on the “Adverse Drug Reaction” form to be reported within 1 working day (24 hours) of learning of the event and proactively reported to the Almirall LLC, CRO Safety Team via email or fax. ADR reporting details will be included in the Safety Reporting Plan.

For the purpose of this study, all AEs that meet the aforementioned definition of an SAE (in Section 8.6.1) that occurred during the treatment period will be reported to the sponsor as SAEs. Upon receipt of SAE data by the study CRO (collected as part of eDCF), they will be reported within 1 working day (24 hours) of learning of the event to the sponsor regardless of its relationship to the study treatment. If any additional information is needed to adequately document the SAEs, the study CRO will follow-up with the Site Investigators to ensure data completeness and will report the updated information back to the study sponsor. If an SAE results in modification of study medication dose or discontinuation of study medication and/or withdrawal of subject from the study, such information will be documented as part of eDCF and reported to the study sponsor.

As part of usual care, Site Investigator will follow Subjects concerning all SAEs and ADRs until adequate resolution or stabilization. If the SAE/ADR has not resolved or stabilized by the time the subject completed the final study visit, the Site Investigator may gather the status of the subject’s SAE/ADR within 30 days beyond the subject’s final study visit, if required.

If a study subject (in case of female) becomes pregnant during the study period, the Site Investigator may withdraw the patient from the study (i.e., early termination) for safety reasons. In this scenario, the Site Investigator will document the reasons for withdrawal in the eDCF and

may conduct necessary follow-ups with the patient to ensure safety, as part of usual care. Occurrence of this (pregnancy) event will be reported to the study sponsor within 1 working day (24 hours) of learning of the event.

In addition, all events with a fatal outcome and all other reportable events (lack of effectiveness of sarecycline, overdose, off-label use, misuse, abuse, medication error or occupational exposure) – even in the absence of an ADR – will be documented on the “Adverse Drug Reaction” form and reported to the study sponsor within 1 working day (24 hours) of learning of the event.

Early terminated patients will be evaluated for safety assessments at the time of next scheduled encounter, as feasible. This will be documented in the eDCF.

